**Table 10.1: Estimated effect size that can be detect with our proposed study with 140 total patients (70 per arm)**

Power	N1	N2	N	Mean1	Mean2	S1	S2	Alpha	Effect size	Alpha
0.80	70	70	140	10	6.20	8	8	3.80	0.475	0.05
0.80	70	70	140	10	5.73	9	9	4.27	0.474	0.05
0.80	70	70	140	10	5.26	10	10	4.74	0.474	0.05

Effect size = (Mean 1 – Mean 2) / S (standardized mean difference).

Note: These results assume that 2 sequential z-test are made using the O'Brien-Fleming spending function to determine the test boundaries. The study will stop early at 50% accrual, for either futility or superiority, if the interim analysis result is significance at  $p < 0.03$ . The nominal significance level at the second test is 0.049. (PASS 14).

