### **10.5 Sample size, accrual and study duration**

Exploratory data analyses on 140 men who underwent radical prostatectomy at the University of Miami (between 2008 and 2012) suggests that men typically drop from a mean SHIM score of 19 at baseline down to approximately a score of 9 one-year post radical prostatectomy. Assuming that the control (no membrane) group will experience declines in SHIM scores similar to this historical cohort, with a mean reduction of 10 SHIM points and a standard deviation on the change scores between the observed 8.5 SD and the pessimistic one sided 80% upper confidence limit of 9.8, and allowing one interim analysis at 50% accrual, our study with 70 patients per group can detect, with 80% power, an effect size of 0.335, as shown in Table 10.1 in this section.. (PASS 14 Power Analysis and Sample Size Software (2015). NCSS, LLC. Kaysville, Utah, USA, [ncss.com/software/pass/](http://ncss.com/software/pass/)) For instance, our proposed study with 70 per group has 80% power to detect a difference of 2.68, between sexual function mean reductions of 10 and 7.32 in treatment groups without and with the membrane respectively, assuming a common standard deviation of 8. As

expected with larger standard deviations only larger absolute differences can be detected with 80% power (See rows 2 and 3 in Table 10.1).

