## 10.7 Interim Monitoring

### 10.7.1 Role of the Research Team and the DSMC

The Research Team will continuously monitor study accruals and adverse events from both treatment arms. Patients will be monitored closely **during treatment and subsequently over 30 days** for any **adverse event** potentially related to treatment. All toxicities, regardless their grade, will be recorded in the patient case report form using NCI/CTEP Common Terminology Criteria for Adverse Events (CTCAE) version 4.03. In addition, a one interim analysis **of the primary efficacy endpoint** is planned in first 50% of study patients.

The Sylvester Comprehensive Cancer Center's Data and Safety Monitoring Committee (DSMC) will monitor this protocol according to the Cancer Center's DSM Plan. In its oversight capacity, the DSMC bears responsibility for suspending or terminating this study.

DSMC oversight of the conduct of this trial includes ongoing review of accrual, adverse event data, and interim analysis of response to treatment. The guidelines appearing in Sections 10.7.2, and 10.7.3 are offered for DSMC consideration in assessing accrual, adverse events, and response to treatment. In addition, the DSMC will review reports from all audits, site visits, or study reviews pertaining to this clinical trial and take appropriate action.

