#### 10.7.3 Interim analysis of the primary efficacy endpoint: change in SHIM scores

While we expect that the membrane will help maintain sexual function, we plan on doing a single interim look at the change in **SHIM scores** and will stop the trial for either futility or superiority of experimental arm 1 based on analysis of 70 men in the treatment and control arms (~35 per arm) have been assessed for sexual function a year following radical prostatectomy. Using an O'Brien Fleming alpha spending rule with a total alpha error rate of 0.05 at the end of the study, an interim look will use a nominal alpha level of 0.003 and the final nominal alpha level will be 0.049.

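### The Table 10.1 note sets the interim stopping threshold at p < 0.03, but Section 10.7.3 sets it at 0.003; only 0.003 fits a total alpha of 0.05 with a final level of 0.049

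*Combined protocol and SAP*

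**What the plan says.** Section 10.5 plans 70 men per arm, "allowing one interim analysis at 50% accrual". The note under Table 10.1 says its results assume that "2 sequential z-test are made using the O'Brien-Fleming spending function to determine the test boundaries". It then states the rule: "The study will stop early at 50% accrual, for either futility or superiority, if the interim analysis result is significance at". The threshold that completes this sentence is printed, together with the level for the final test, as "p < 0.03$ . The nominal significance level at the second test is 0.049".

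Section 10.7.3 describes the same single look, triggered when 70 men (about 35 per arm) have been assessed one year after surgery. It says the sponsor "will stop the trial for either futility or superiority of experimental arm 1". It sets total alpha at 0.05 under O'Brien-Fleming spending, and for the two tests it states that "an interim look will use a nominal alpha level of 0.003 and the final nominal alpha level will be 0.049".

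Section 10.7.1 tells the monitoring committee where to look: "The guidelines appearing in Sections 10.7.2, and 10.7.3 are offered for DSMC consideration". The opening of Section 10 also points to Section 10.7.3 for the interim analysis. Neither section says whether the levels are one-sided or two-sided.

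**The concern.** Two current parts of the plan give different thresholds for the only efficacy stopping decision in the trial, and nothing explains the difference. The note is worded as a rule to be followed, so an interim p-value between 0.003 and 0.03 would stop the trial under one section and continue it under the other. If the note were applied and the final test still run at 0.049, the type I error would exceed the stated 0.05, and the trial could stop for superiority on a smaller observed difference than planned.

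A secondary problem is the word futility. The Table 10.1 note ties it directly to a significance threshold, and Section 10.7.3 names it just before giving the same kind of levels. Neither gives a futility boundary. A disappointing, non-significant interim result cannot meet a p < 0.003 rule. The word may mean stopping for a significant result against the membrane, but the text does not say so.

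**Working it through.** **Inputs.** From Table 10.1 and its note: 70 per arm; differences 3.80, 4.27 and 4.74 at SD 8, 9 and 10; power 0.80; two z-tests with O'Brien-Fleming spending. From Section 10.7.3: total alpha 0.05; look at 70 of 140 men, so information fraction t = 0.5; levels 0.003 and 0.049. Sidedness is not stated and is taken as two-sided (see step 5).

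**Method.** The interim and final z-statistics are bivariate normal with correlation √0.5 = 0.7071. For nominal levels a₁ and a₂ with two-sided critical values c₁ and c₂, the probability of rejecting is 1 − P(|Z₁| < c₁ and |Z₂| < c₂). Under the null both means are 0. For a difference d, the final mean is θ = d / (SD·√(2/70)) and the interim mean is θ·√0.5.

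**1. Reproduce the plan's power with 0.003/0.049.** For row 1, θ = 3.80 / (8 × 0.1690) = 2.81. Power in the three rows is 80.1%, 80.0% and 79.9%. The smallest standardized difference with 80% power is 0.4744, which gives 3.80, 4.27 and 4.74 points. This matches Table 10.1 to the printed digits.

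**2. What the named spending function gives.** With 0.025 per tail at t = 0.5, the two-sided interim level is 4 × [1 − Φ(2.2414 / 0.7071)] = 0.00305. The final level that brings the total to 0.05 is then 0.0490. This is the Section 10.7.3 pair. Conversely, with the final level fixed at 0.049, the largest interim level that keeps the total at 0.05 is 0.00305.

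**3. Compare the two thresholds.**

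| Interim / final level | Overall two-sided alpha | Superiority direction | Power, three rows | Differences at 80% power |
|---|---|---|---|---|
| 0.003 / 0.049 | 0.04998 | 0.0250 | 80.1, 80.0, 79.9% | 3.80, 4.27, 4.74 |
| 0.03 / 0.049 | 0.0670 | 0.0335 | 81.3, 81.2, 81.1% | 3.74, 4.20, 4.67 |
| 0.03 / 0.0288 (in neither section) | 0.0500 | – | 75.7, 75.6, 75.5% | 4.00, 4.50, 5.00 |

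The last row shows what keeping 0.03 and a total alpha of 0.05 would require: a final level that contradicts both sections. A simulation of 4 million trials under the null gave 0.0502 and 0.0672 for the first two rows.

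**4. Observed difference needed to stop at the interim,** z(1 − a₁/2) × SD × √(2/35), where √(2/35) = 0.2390 and z is 2.968 for 0.003 and 2.170 for 0.03:

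| SD | Stop at 0.003 | Stop at 0.03 |
|---|---|---|
| 8 | 5.68 | 4.15 |
| 9 | 6.38 | 4.67 |
| 10 | 7.09 | 5.19 |

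If the true standardized difference is 0.475, the chance of stopping at the interim is 16.3% with 0.003 and 42.7% with 0.03.

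**5. Other readings.** If the levels are read as one-sided, overall alpha is 4.97% with 0.003/0.049 and 6.49% with 0.03/0.049. That reading gives 87.7% power in row 1 with 0.003/0.049, so the table itself points to two-sided levels. The classical O'Brien-Fleming boundary gives 0.0052/0.0480, and spending the function on 0.05 in total gives 0.0056/0.0478. Neither is near 0.03.

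**The case against.** - **The practical risk is small.** Section 10.7.3 is the operative interim section and has the fitting value. Both Section 10.7.1 and the opening of Section 10 direct the reader there, and nothing directs anyone to a note under a sample-size table. The 6.7% arises only if that note is applied instead. This stands, and it limits the weight of the point. It does not remove a contradiction between two current statements of the same rule.
- **Power hardly separates the two values.** The pair as printed in the note gives about 81%, close to the stated 80%. This also stands: 0.03 does not make the power fail, and the 75.5–75.7% figures belong to a pair that the plan never states. The case rests on alpha. Power adds only that 0.003 returns the table's differences exactly and 0.03 does not.
- **Futility and the accrual wording are separate matters.** This is fair. They are clarifications of the same rule, and the correction of the threshold does not depend on them. Section 10.7.3 already defines the trigger adequately.

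**Conclusion.** The concern holds. The 0.03 in the Table 10.1 note is inconsistent with Section 10.7.3, with the named spending function and with the stated total alpha; it appears to have lost a zero. Used with the final level of 0.049, it would raise the overall two-sided type I error from 5.0% to 6.7% (2.5% to 3.35% in the superiority direction) and lower the stopping difference by 1.5 to 1.9 SHIM points across SD 8 to 10 (5.68 − 4.15 = 1.53; 7.09 − 5.19 = 1.90).

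These figures assume a look at exactly half the information, two-sided levels, normal test statistics and complete 12-month data on 70 men per arm. The conclusion does not depend on sidedness. The correction should be made, but sample size and power are sound on this point because the table was evidently computed with 0.003/0.049.

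**What to change.** 1. In the note under Table 10.1, change the interim threshold from 0.03 to 0.003.
2. In that note and in Section 10.7.3, state that the nominal levels are two-sided.
3. In both places, remove futility from the significance rule, or reword it as stopping for a significant difference in either direction if that is what is meant. A separate non-binding futility rule is optional.
4. For consistency, replace the 50% accrual wording in Section 10.5 and the note, and the similar wording in Section 10.7.1, with the Section 10.7.3 trigger of 70 men assessed for SHIM at 12 months.

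The cost is protocol wording only, with no change to sample size, power or the Section 10.7.3 boundary. The change should be made before any interim efficacy data are seen, so that the threshold cannot be disputed afterwards.

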## 10.6 Statistical Analysis

The difference in the SHIM score decline in each group from baseline to 12 months post RARP with 95% CIs will be reported as the primary endpoint for the study. Linear regression models will be fitted to determine the likely decline in SHIM scores based on receipt of a membrane during RARP. These models will control for baseline SHIM scores, age, and a binary indicator of the use of any oral erectile aids, in addition to other important demographic and clinic factors.

Among men with a SHIM greater than or equal to 17, the proportion of men in each group with a SHIM of 17 or greater, able to achieve an erection sufficient for intercourse more than 50% of the time, or not requiring any invasive erectile aids at each follow up interval will be reported and compared using counts and percentages with 95% CLs. Logistic regression models will be fitted to determine the likelihood of having achieving each result controlling for age and a binary indicator of the use of any oral erectile aids, in addition to other important demographic and clinic factors. Both unadjusted and adjusted odds ratios with 95% CIs and their corresponding p-values will be reported

In addition, we will report by treatment group adverse event rates by grade and attribution, and the number and percentage of men not needing pads.

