#### **4.4 Follow Up and Analyses**

Patients will be followed up every three months ( $\pm$  1 month) for a total of one year. This follow up schedule meets the current standard of care after radical prostatectomy. At each follow up a serum PSA will be assessed for recurrence on prostate cancer. To investigate primary and secondary endpoints a self-reported validated questionnaire will be provided assessing measures of potency. Finally, the use of pads for urinary leakage will be

assessed at each time point. After the first year, there will be annual follow up with PSA measurements and an assessment of any secondary therapies for 5 years. Further details regarding the primary and secondary endpoints can be found in Section 3. The analyses will be performed as an intention to treat analysis. More details regarding the analyses of primary and secondary endpoints can be found in Section 10.

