### **5.7 Cancellation Guidelines**

The following are reasons for withdrawal of subjects from the study:

- A subject does not meet the eligibility criteria, (the subject will be considered a screen failure).
- A subject withdraws consent,
- A subject dies during protocol participation or
- A study investigator decides the subject should be withdrawn from the study (e.g. subject non-compliance)

Regardless of reason for withdrawal, once a patient has been randomized to an arm, an intention to treat analysis will be performed.

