## 10. STATISTICAL CONSIDERATIONS

This is a blinded two-arm randomized phase 2 trial. Patients will be randomized in a ratio 1:1 to study arms, the experimental Arm I (membrane placement) and control Arm II (no membrane placement, standard of care surgery), using a permuted block design stratified by baseline SHIM score (<17 vs. >=17), and use of ANY erectile aids (Yes vs. No) in the last 3 months.

All analyses will be performed as an intention to treat and as per Protocol. Although there is no data to suggest an increased risk of any potential adverse effects with placement of a sling, we will monitor adverse events as per section 10.7.2. An interim analysis of the primary efficacy endpoint, change in SHIM score, will be performed as part of the analysis plan as described in section 10.7.3..

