### 10.1 Primary Study Endpoints

The difference in average change in SHIM score, between baseline and 12 months post RARP between the membrane and control arms will be assessed as the primary endpoint.

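### The plan promises intention to treat but gives no rule for a missing 12-month SHIM; by default the regression uses completers only and ignores the interim SHIM scores.

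*Combined protocol and SAP*

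**What the plan says.** - **Endpoint (Section 10.1).** The primary endpoint is "The difference in average change in SHIM score, between baseline and 12 months post RARP between the membrane and control arms".
- **Model (Section 10.6).** The between-group difference in decline is reported with 95% confidence intervals. The plan adds that "Linear regression models will be fitted to determine the likely decline in SHIM scores", with the arm effect worded by whether a man received a membrane, and that "These models will control for baseline SHIM scores, age, and a binary indicator of the use of any oral erectile aids", plus other factors that are not named. No interim SHIM score enters.
- **Population.** Section 4.4 states "The analyses will be performed as an intention to treat analysis". Section 5.7 is more explicit: "Regardless of reason for withdrawal, once a patient has been randomized to an arm, an intention to treat analysis will be performed". Section 7.3 repeats the promise for men who discontinue and says they are followed for clinical data, without saying whether SHIM is included. Section 10 says "All analyses will be performed as an intention to treat and as per Protocol", and neither set is defined.
- **Interim SHIM scores.** Section 7.2 lists SHIM at 0, 3, 6 and 12 months. Appendix I also marks month 9, and the secondary endpoints in Section 10.2 need it. The post-baseline scores before month 12 serve only those secondary endpoints, in men with a baseline SHIM of 17 or more.
- **Missing data.** No section gives an imputation method, a repeated-measures model, a missing-data sensitivity analysis or a dropout allowance.

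**The concern.** A man without a 12-month SHIM has no value for the outcome being regressed. Unless something is added, standard software drops him, and the set analysed is no longer everyone randomised. Two things are then at stake.

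The first is power. Table 10.1 treats the 70 men randomised per arm as 70 men analysed, so any loss comes straight off the planned 80%.

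The second is bias. The outcome is a self-reported questionnaire about erectile function, and men who recover poorly may be less likely to return it. If that tendency differs between arms, completers are no longer comparable.

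Scores at 3 and 6 months are scheduled in every version of the calendar and would carry information about a missing 12-month value. The silence also leaves the choice of method open until after data, including the interim look, have been seen.

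**Working it through.** **Inputs from the documents.** 70 per arm; difference 3.80 and SD 8, so effect size 0.475 (Table 10.1, row 1); nominal levels 0.003 and 0.049 (Section 10.7.3).

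**Assumptions, because the documents are silent.** Loss of 10% to 20%; correlation 0.7 between months 9 and 12; log-odds of loss rising by 0.5 to 1.5 for each SD of poorer month-9 score.

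**1. The plan's own figure.** Power is Φ(0.475 × √(n/2) − 1.96). With n = 70: 0.475 × 5.916 = 2.810, and Φ(0.850) = 0.802. The two-look calculation gives 0.801. Table 10.1 therefore reproduces. The 0.335 in the text of Section 10.5 does not (power about 51%); that is a separate matter, and the table is used here.

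**2. Loss unrelated to score, completers only.**
- 10% lost: n = 63, Φ(2.666 − 1.96) = 0.760.
- 20% lost: n = 56, Φ(2.513 − 1.96) = 0.710.

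**3. The same loss, using month 9.** With a fraction d lost, the variance of the month-12 mean rises by the factor (1 − 0.49)/(1 − d) + 0.49.
- d = 0.10: factor 1.057, effective n = 66.2, power 0.78.
- d = 0.20: factor 1.1275, effective n = 62.1, power 0.75.

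The gain is about 2 and 4 points. Simulations of the same situation gave 2 to 6.

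**4. Poor recovery drives loss, same rule in both arms.** With no true effect the arms are distorted equally and the bias is 0. With a true difference of 3.8, slightly more controls are lost. The bias is -0.06 points at 10% loss and slope 0.5, and -0.49 at 20% loss and slope 1.5: about -0.1 to -0.5, toward no effect.

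**5. Poor recovery drives loss in the control arm only**, with the same percentage lost at random in the membrane arm. Let m be the mean standardised month-9 score of the retained controls. The control mean at month 12 is then too high by 0.7 × 8 × m = 5.6m, and the arm difference is biased by -5.6m.
- 10% loss, slope 0.5: m = 0.049, bias -0.27. The standard error is 8√(2/63) = 1.425. Type I error is Φ(−1.96 + 0.19) + Φ(−1.96 − 0.19) = 5.4%. Power is Φ(3.53/1.425 − 1.96) = 70%.
- 20% loss, slope 1.5: m = 0.227, bias -1.27. The standard error is 8√(2/56) = 1.512. Type I error is Φ(−1.96 + 0.84) + Φ(−1.96 − 0.84) = 13.4%. Power is Φ(2.53/1.512 − 1.96) = 39%.

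The extra rejections fall on the side favouring control. A large-sample simulation with correlation 0.8, and up to 24% of controls lost, gave -0.5 to -1.7 points.

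**6. What the interim scores can repair.** When the observed month-9 score explains the loss, the likelihood estimate has bias of about 0. When loss depends on the unseen month-12 score, up to -0.3 points remained. With a steep control-only rule (slope 2) and half of the lost men also lacking month 9, about -0.3 points remained at 10% loss and -0.6 at 20%, less than half of the completers-only bias.

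**The case against.** **The text does not say that men are dropped.** A reader might infer from Section 10.6 that the plan restricts the analysis to men with a 12-month SHIM, or that intention to treat has been abandoned. Neither is written. Multiple imputation followed by the same regression would fit the wording. The completers-only analysis is the default when nothing else is specified, and that is all that can be claimed.

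**The regression is not labelled the primary test.** Section 10.6 names the difference in decline as the primary result and then lists the models. This is fair, but it does not help: a raw difference in 12-month change also needs a 12-month score.

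**Loss may be small.** The membrane is placed once, at surgery, and visits follow standard care, so a man who stops participating may still supply data. This stands as a reason not to assume a high rate. However, Section 5.7 allows withdrawal of consent and withdrawal by the investigator, and Section 7.3 does not say that SHIM continues.

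**Bias is not automatic.** A reader might infer that dropout after poor recovery always biases the comparison or inflates type I error, or that it flatters the membrane. With the same rule in both arms and no effect it does none of these. With a control-only rule the error goes against the membrane. Section 10 calls the trial blinded, which makes an arm-specific rule less likely, although it does not say who is blinded.

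**The remedy is not unique.** This is accepted: multiple imputation using the interim scores would serve as well.

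**Conclusion.** The gap is real and worth closing, but it is an omission with a poor default, not a stated exclusion. Nothing in the documents says how a man without a 12-month SHIM enters the promised analysis, and the interim scores are unused in the primary result.

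The firmest consequence is lost power: from 80% to about 76% or 71% at an assumed 10% or 20% loss, of which a few points are recoverable at no cost in patients. Bias is conditional. It is small (at most about half a point of 3.8) if the loss rule is common to both arms. It becomes serious, at up to about 1.3 points or a third of the planned difference (1.3/3.8 = 34%), only with a steep rule confined to the control arm. The documents do not establish such a rule. Every one of these sizes rests on the assumed loss, correlation and mechanism.

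Section 10.6 also words the arm effect by receipt of the membrane, which sits badly with intention to treat and should be corrected in the same edit.

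**What to change.** Before any unblinded look, including the interim analysis, amend Section 10.6 as follows.

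1. Define the intention-to-treat set as all randomised men, analysed by randomised arm and not by receipt of the membrane.
2. Make the primary analysis a likelihood-based repeated-measures model of all scheduled post-baseline SHIM scores. Include arm, visit, arm by visit, baseline SHIM by visit, age and the erectile-aid stratum, with unstructured covariance. The month-12 arm contrast is the primary result. Multiple imputation using the interim scores is an acceptable alternative.
3. Keep the 12-month regression as a sensitivity analysis, and add one missing-not-at-random analysis.
4. Reconcile Section 7.2, which omits SHIM at month 9, with Section 10.2 and Appendix I, which include it. State whether SHIM is still sought from men who discontinue.

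The cost is SAP wording and a little more analysis work, with no added patients. The limit is that the model still assumes missing at random, so it removes bias only as far as the observed scores explain the loss. Item 3 is there for the remainder.

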#### **4.3 Study Randomization**

Randomization of study patients will be done in equal proportion to Arm I (membrane placement) and Arm II (no membrane placement, standard of care surgery) using a permuted block design stratified by baseline SHIM score (<17 vs.  $\geq 17$ ), and use of **ANY** erectile aids (Yes vs. No) in the last 3 months.

Randomization lists for each stratum will be prepared by SCCC Biostatistics prior to the first patient enrollment and provided to the SCCC CRS-Informatics office where they will be programmed and customized as per randomization requirement using the CIERRA system. Members of the study team, including those responsible for patient enrollment, will not have access to the randomization lists.

After each patient's study eligibility is confirmed and the informed consent is signed, CRS coordinators will enter the required patient information into the CIERRA system in order to register the patient. The CRS coordinators will receive the designated patient ID, study arm, randomization number, and randomization date. CRS coordinators will print the randomization confirmation form from the CIERRA system and place it in the patient's research chart and then notify the requesting member of the study team of the treatment assignment for the new randomized patient.

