### **7.3 Early discontinuation of study participation**

Subjects that discontinue participation in part of or all the interventions in this study due to progression or other (patient or physician decision) reasons will be followed for clinical data and analyzed by intention to treat. Those who experience a biochemical or clinical recurrence and undergo radiation will be analyzed by intention to treat and their analysis adjusted for the receipt of secondary treatments. There will be no stopping rules for safety, as previous observational studies have suggested no increased risk of any adverse events with placement of membranes during the surgery. All adverse events will still be reported, as discussed in Section 8.

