### **10.4 Endpoint definitions**

- Potency as measured by well-validated questionnaires: SHIM and EPIC 26. A SHIM greater than or equal to 17 defines mild ED or better
- Urinary continence or control is defined as no pads per day
- Recurrence post-radical prostatectomy defined as a PSA > 0.2 ng/ml on 2 or more consecutive reads or the receipt of any salvage therapy.

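### Does wording the SHIM-decline regression by membrane receipt turn the primary comparison into an as-treated analysis?

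*Combined protocol and SAP*

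**What the plan says.** Section 10.1 defines the primary endpoint as the difference in average SHIM change from baseline to 12 months "between the membrane and control arms will be assessed as the primary endpoint". Section 10.6 first commits to reporting that difference by group with 95% confidence intervals. It then adds linear regression models to "determine the likely decline in SHIM scores based on receipt of a membrane during RARP", adjusted for baseline SHIM, age, use of oral erectile aids and other factors. The logistic models that follow, one of which concerns SHIM of 17 or more, are not worded by receipt.

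On the analysis principle, section 4.4 says: "The analyses will be performed as an intention to treat analysis". Section 5.7 says that, whatever the reason for withdrawal, "once a patient has been randomized to an arm, an intention to treat analysis will be performed". Section 7.3 says that men who have a recurrence and undergo radiation will be "analyzed by intention to treat and their analysis adjusted for the receipt of secondary treatments". The introduction to section 10 says: "All analyses will be performed as an intention to treat and as per Protocol". No section defines a per-protocol set.

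**The concern.** *Receipt* normally means what a patient actually got, and the document uses it that way elsewhere: for secondary treatments in section 7.3, and in the recurrence definition in section 10.4 ("2 or more consecutive reads or the receipt of any salvage therapy"). If section 10.6 is read the same way, the only regression named for SHIM decline compares men by treatment received.

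Allocation and receipt can differ. The arm is assigned at registration (section 4.3: "After each patient's study eligibility is confirmed and the informed consent is signed"), whereas the membrane is placed later, during the operation (section 5.2). If the reasons for a departure were related to prognosis, a model coded from operative records would lose the protection of randomisation for those men. The per-protocol phrase in section 10 appears to add to the problem, because nothing there says which result leads if two analyses disagree.

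**Working it through.** The question is mainly one of reading, so the relevant places are set side by side first. The arithmetic then shows what can and cannot be said about size.

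1. **Which contrast is primary.** Section 10.1 compares arms. The first sentence of section 10.6 reports the difference by group and identifies it as the primary endpoint. The regression comes after this as an adjusted model and is not itself called primary.

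2. **What the design was sized on.** Table 10.1, row 1, takes 70 men per arm, a difference of 3.80 and SD 8. The standard error is 8 × √(2/70) = 1.352, and 3.80/1.352 = 2.81. At two-sided 0.05 the power is Φ(2.81 − 1.96) = 0.80, which matches the table. The 70 per arm are the men *allocated* (section 4.1), so the sizing is by arm as well.

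3. **What *receipt* can mean.** In sections 7.3 and 10.4 it refers to later therapies that nobody was randomised to, so there it can only mean actual receipt. Those uses do not settle its meaning for the randomised treatment. For that, the document names the arms by the procedure: sections 4.3 and 10 label Arm I by membrane placement and Arm II by its absence, and section 10.5 speaks of groups with and without the membrane. The phrase in section 10.6 fits that habit.

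4. **The per-protocol phrase.** It may mean only that analyses follow the protocol, in which case it is redundant. It may instead mean an additional per-protocol analysis, in which case its set is undefined. On either reading intention to treat is still required, by that sentence and by sections 4.4, 5.7 and 7.3.

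5. **Size if the phrase were applied literally.** Suppose there is no true effect and the residual SD is s. A share a of Arm I has no membrane, with prognosis shifted by dI (in SD units). A share b of Arm II has one, with shift dII. Fixing each arm mean at zero,

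   bias = s × (b·dII − a·dI) × [1/(1 − a + b) + 1/(1 + a − b)].

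   With s = 8:
   - a = b = 0: 0.
   - a = 7/70, dI = −0.5, b = 0: 8 × (0.05/0.9 + 0.05/1.1) = +0.81 SHIM points.
   - b = 7/70, dII = −0.5, a = 0: −0.81.
   - a = b = 7/70, both shifts −0.5: 0.
   - a = b = 7/70, dI = −0.5, dII = +0.5: 8 × 0.10 × 2 = +1.60.

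   Every non-zero a, b and d here is an assumption, because the documents give none of them. Using 8 as a residual SD is also an assumption: in Table 10.1 it is the SD of change scores, and section 10.5 gives 8.5 as the observed value. The result can take either sign or vanish, and 0.81 is not an upper limit. The formula shows that literal coding could matter, but it yields no estimate for this trial. The by-arm coefficient has expectation 0 in every case.

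**The case for a change.** The strongest case for a change is that section 10.6 is the model specification an analyst would follow. As worded, it could be taken to permit coding treatment from operative records, and section 10 offers no ranking if arm-based and receipt-based results differ. Such choices are best fixed before data are seen, and the cost would be one phrase and one sentence. Departures are also conceivable: section 7.3 foresees men discontinuing part of the intervention, and section 1.4 says patients have been asking for membranes.

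Part of this stands. The wording is imprecise, no per-protocol set is defined, and no sentence ranks the two analyses. The step from there to a changed result does not stand. To fit the model by receipt as the main analysis, an analyst would have to set aside four intention-to-treat statements and an arm-based endpoint on the strength of one phrase. The remark in section 1.4 concerns patients in general, outside the trial, and section 10 describes the trial as blinded, which would make crossover at a patient's request less likely.

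**Conclusion.** The wording is loose, but the plan is not defective on this point. The arm-based primary endpoint, the group comparison that opens section 10.6 and the repeated intention-to-treat commitments fix the comparison as one by randomised arm. Sharper wording would leave the analysis, sample size and results as they are. A per-protocol analysis, if run, would need its set described when reported and would sit beside the intention-to-treat result without replacing it.

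The effect is zero if all men receive their allocated procedure. It is also zero for the primary comparison whenever the model is coded by arm, whatever the departures. This conclusion assumes that analysts read section 10.6 together with sections 4.4, 5.7, 7.3, 10 and 10.1. No bias in SHIM points should be attached to the concern, because the documents supply neither a departure rate nor any indication of how men who depart would differ.
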